4.4.2 Dose Escalation

The investigator will comprehensively examine the blinded safety results (AEs, physical examinations, vital signs, records of laboratory tests, and 12-lead ECG findings) obtained at all examinations by 14 days after the start of study drug administration in Cohort 1 and then determines the entry of Cohort 2 after discussion(s) with the Sponsor, and if appropriate, with medical experts.

Other criteria to consider discontinuation of the entry of Cohort 2 are as follows.

1. On an occasion that a SAE, of which relationship to the study drug cannot be denied, is observed.

TAK-906-1004	Page 10 of 33
Statistical Analysis Plan	10 Nov 2017

2. At the onset of an AE for which relationship to the study drug cannot be denied and for which it is considered difficult to give medications continuously.

Furthermore, the maximum dose in this study was set at 100 mg BID for Cohort 2, based on the data from preceding studies, as described in Section 6.3.2 of protocol. Dose level in Cohort 2 may be changed within the range up to 100 mg, as appropriate, based on the safety and pharmacokinetic data of preceding cohorts, ie, 50 mg BID in Cohort 1 or 10 mg BID in Cohort 3 (if applicable) of this study.

5.0 ANALYSIS ENDPOINTS

5.1 Primary Endpoint

The study's primary endpoints of safety and tolerability will be assessed through TEAEs including QTc prolongation associated AE, neurologic AE, and hyperprolactinemia associated AE, physical examinations, vital signs, clinical laboratory tests, and 12-lead electrocardiogram (ECG).

5.2 Secondary Endpoints

Secondary endpoints include:

- 1. PK: Plasma and urine concentrations of TAK-906 and its metabolite, M23.
- 2. PD: Serum prolactin level.

6.0 DETERMINATION OF SAMPLE SIZE

A sample size of 8 subjects per cohort (6 active: 2 placebo) will be used in this study, and is considered sufficient for the evaluation of TAK-906 safety, tolerability, PK and PD following oral single and multiple doses. The sample size is not based on statistical power considerations.

7.0 METHODS OF ANALYSIS AND PRESENTATION

7.1 General Principles

7.1.1 Study Definitions

The following definitions and calculation formulas will be used.

- TEAE: An AE whose date of onset occurs on or after the start of study drug. A TEAE whose relationship to study drug is missing will be considered drug-related. A TEAE whose intensity is missing will be considered severe.
- PTE: An AE whose date of onset occurs before the start of study drug..
- Descriptive statistics: number of subjects with non-missing values, mean, standard deviation, maximum, minimum, and quartiles, including geo-mean, geo-CV as needed
- QTcF interval (msec): QT interval (msec) / (RR interval (msec)/1000)^{0.33} (rounded to the nearest whole number)
- Baseline values: The last evaluable observation (ie, non-missing) before the first dose of study drug. If no evaluable observation is obtained before the first dose, the baseline value will be missing.
- TEAE occurred in single dose period: A TEAE occurred prior to start of multiple dosing.
- TEAE occurred in multiple dose period: A TEAE occurred from Day 3 postdose through Day 14 (follow-up visit).

7.1.2 Definition of Study Days

Study Day: The day before the first dose of the study drug will be defined as Study Day -1 and the day of the first dose will be defined as Study Day 1. Other study days are defined relative to Study Day 1, eg, the day 2 days prior to Study Day 1 is Day -2 and the day after Study Day 1 is Day 2.

7.1.3 Definition of Study Visit Windows

The baseline visit is defined as the period before the first dose of study drug, and post-baseline visits are defined in line with CRF-recorded visits. The last evaluable observation (ie. non-missing) in the baseline visit will be used as the baseline value, and all evaluable observation will be used for each post-baseline visit.

7.1.4 Method of Data Conversion and Handling of Missing Data

No imputation of missing data or of excluded data will be applied. Values below the lower limit of quantification will be handled as 0.

7.2 Analysis Sets

The Safety Analysis Set will be defined as all subjects who received at least one dose of the study drug.

The PK Analysis Set will consist of subjects who received at least one dose of the study drug, completed the minimum protocol specified procedures with no significant protocol deviations which are listed below, and were evaluable for the pharmacokinetics.

- Subjects who did not meet inclusion criteria #3or #4
- Subjects who met exclusion criteria #1, #4, #5, #6, #7, #9, #10, #12, #13, #15, #17, #18, #19, #23 or #25

The PD Analysis Set will consist of subjects who received at least one dose of the study drug, completed the minimum protocol specified procedures with no significant protocol deviations which are listed below, and were evaluable for the pharmacodynamics.

- Subjects who did not meet inclusion criteria #3or #4
- Subjects who met exclusion criteria #1, #4, #5, #6, #7, #9, #10, #12, #13, #15, #17, #18, #19, #23 or #25

7.3 Disposition of Subjects

7.3.1 Study Information

All Subjects Who Signed the Informed Consent Form	
Date First Subject Signed Informed Consent Form	
Date of Last Subject's Last Visit/Contact	
MedDRA Version	
SAS Version Used for Creating the Datasets	
(1) Study Information	
Study information shown in the analysis variables section will be provided.	

7.3.2 Screen Failures

Analysis Set: All Subjects Who Did Not Enter the Treatment Period
 Analysis Variables: Age (years) [Min<= - <30, 30<= - <40, 40<= - <=Max]
 Analytical Methods: (1) Screen Failures

 Frequency distributions for categorical variables and descriptive statistics for continuous variables will be provided.

7.3.3 Subject Eligibility

Analysis Set:	All Subjects Who Signed the Informed Consent Form		
Analysis Variables:	Eligibility Status	[Eligible for Randomization, Not Eligible	
		for Randomization]	
	Primary Reason for Subject Not Being Eligible	[Adverse Event, Death, Lost to Follow-	
		Up, Protocol Deviation, Sample Size	
		Sufficient, Screen Failure, Study	
		Terminated by Sponsor, Withdrawal by	
		subject, Other]	
Analytical Methods:	(1) Eligibility for Entrance into the Treatment Period		
	Frequency distributions will be provided.	When calculating the percentages for the	

Frequency distributions will be provided. When calculating the percentages for the primary reasons for subject not being eligible, the total number of ineligible subjects will be used as the denominator.

7.3.4 Disposition of Subjects

Analysis Set:	Randomized Set	
Analysis Variables:	Study Drug Administration Status	[Randomized but Not Treated]
	Reason for Not Being Treated	[Adverse Event, Death, Lost to Follow-Up,
	-	Protocol Deviation, Study Terminated by
		Sponsor, Withdrawal by subject, Other]
	Study Drug Completion Status	[Completed Study Drug,
		Prematurely Discontinued Study Drug]
	Reason for Discontinuation of Study Drug	[Adverse Event, Death, Lost to Follow-Up,
		Protocol Deviation, Study Terminated by
		Sponsor, Withdrawal by subject, Other]
Analytical Methods:	(1) Disposition of Subjects	
	Frequency distributions will be prov	ided by dose and overall. When calculating

Frequency distributions will be provided by dose and overall. When calculating percentages for the reasons for not being treated, the total number of subjects not treated by the study drug will be used as the denominator. When calculating percentages for the reasons for discontinuation of study drug, the total number of subjects who prematurely discontinued the study drug will be used as the denominator.

7.3.5 Protocol Deviations

Analysis Set:	Randomized Set	
Analysis Variables :	Protocol Deviation	[Entry Criteria, Concomitant Medication, Procedure Not
		Performed Per Protocol, Study Medication, Withdrawal Criteria,
		Major GCP Violations]
Analytical Methods :	(1) Protocol Deviation	S

Frequency distribution will be provided by dose and overall for each deviation category. A subject who has several deviations will be counted once in each appropriate category. A subject who has several deviations that can be classified into the same category will be counted only once.

7.3.6 Analysis Sets

Analysis Set:	Randomized Set	
Analysis Variables:	Handling of Subjects	[Entry Criteria]
	and Subject Data Analysis Sets	
	Safety Analysis Set	[Included, Excluded]
	PK Analysis Set	[Included, Excluded]

	PD Analysis Set	[Included, excluded]
Analytical Methods:	(1) Analysis Sets	
	Frequency distribu	tions will be provided by dose.

7.4 Demographic and Other Baseline Characteristics

Analysis Set:	PK Analysis Set		
	PD Analysis Set		
	Safety Analysis Set		
Analysis Variables:	Age (years)	[Min<= - <30, 30<= - <40, 40<= - <=Max]	
	Height (cm)	[Min<= - <150, 150<= - <160,	
		160<= - <170, 170<= - <=Max]	
	Weight (kg) (Baseline)	[Min<= - <50.0, 50.0<= - <60.0,	
		60.0<= - <70.0, 70.0<= - <80.0,	
		80.0<= - <=Max]	
	BMI (kg/m ²) (Baseline)	[Min<= - <18.5, 18.5<= - <=25.0,	
		25.0< - <=Max]	
	Smoking Classification	[Never, Current, Former]	
	Consumption of Alcohol	[Daily, A Few Times Per Week, A Few Times Per	
		Month, No]	
	Consumption of Caffeine	[Yes, No]	
Analytical Methods:	(1) Summary of Demographics and Other Baseline Characteristics		
	Frequency distributions for categorical variables and descriptive statistics for		
	continuous variables will be provided by dose and overall.		

7.5 Medical History and Concurrent Medical Conditions

There will be no analysis of medical history and concurrent medical conditions.

7.6 Medication History and Concomitant Medications

There will be no analysis of medication history and concomitant medications.

7.7 Study Drug Exposure and Compliance

Not applicable

7.8 Efficacy Analysis

Not applicable

7.9 Pharmacokinetic/Pharmacodynamic Analysis

7.9.1 Pharmacokinetic Analysis

7.9.1.1 Plasma Concentrations of TAK-906 and M23

Analysis Set: Analysis Variable: Time Point:	PK Analysis Set except subjects with placebo Plasma Concentrations of TAK-906 and M23 Visit: Days 1 and 7
	Pre-morning dose (0 hours) and 0.5, 1, 1.5, 2, 3, 4, 6, 8, 12, 16, 24 hours post-morning dose (relative to start time of morning dose at Day 1 or 7)
	Visit: Days 3-6
	Pre-morning dose (0 hours)
Analytical Methods:	 The following summaries will be provided for each analyte by dose. (1) Summary of Plasma Concentrations by Time Point Descriptive statistics for observed values will be provided for each time point. In addition, geometric mean, geometric standard deviations, and %CV will be provided (2) Concentration-time Profiles for Individual Subjects Observed values will be plotted using individual case plot. (3) Mean Concentration-time Profiles with Standard Deviations Mean of plasma concentration will be plotted by time point using linear scale for Days 1-7, Day 1 and Day 7 respectively. (4) Geometric Mean of plasma concentration will be plotted by time point using natural log scale for Days 1-7, Day 1 and Day 7 respectively.

7.9.1.2 Plasma PK Parameters of TAK-906 and M23

Analysis Set:	PK Analysis Set except subject with placebo			
Analysis Visit and				
Variable:	Plasma Concentrations of TAK-906 and M23			
	Visit: Day 1			
	C _{max}	t _{max}	AUC_{∞}	
	AUC _{last}	AUC ₂₄	AUC_{τ}	
	t _{1/2z}	λ_z	CL/F (TAK-906 only)	
	V _z /F (TAK-906 only)	$MRT_{\infty,ev}$		
	Visit: Day 7			
	C _{max,ss}	t _{max,ss}	$AUC_{\tau,ss}$	
	t _{1/2z}	λ_z	CL/F _{ss} (TAK-906 only)	
	V_z/F_{ss} (TAK-906 only)	$\mathrm{MRT}_{\infty,\mathrm{ev}}$	C _{av,ss}	

	C _{min,ss}	t _{min,ss}	PTF%
	$R_{ac(AUC)}$	$R_{ac(Cmax)}$	
Analytical Methods:	The following summa	ries will be provided for eac	h analyte by dose.
	(1) Summary of Plasma PK Parameters		
	Descriptive statistics for PK parameters will be provided. In addition, geometric mean and %CV will be computed for C_{max} and AUCs.		
	(2) Exposure versus Scatter plot will	dose plots be created with the X axis a	s dose levels and Y axis as C_{max} or AUCs.
	(3) Dose-normalized exposure versus dose plots		
Plots of dose-normalize individual subjects data		rmalized Cmax and AUCs v ts data.	ersus dose levels will be prepared with
	(4) Dose proportionality		
	Dose proportiona and power model	ality of C_{max} and AUCs acro .	ss dose levels will be assessed using linear

7.9.1.3 Urine PK Parameters of TAK-906 and M23

Analysis Set:	PK Analysis Set except subject with placebo			
Analysis Visit and	Urine PK Parameters	of TAK-906 and M23, and	the Total of TAK-906 and M23	
Variable:				
	Visit: Day 1			
	Ae ₂₄	$f_{e,24}$	CL_R	
	Visit: Day 7			
	Ae _τ	$f_{e, \tau}$	CL_R	
Analytical Methods:	The following summaries will be provided for each analyte by dose.			
	(1) Summary of Urine PK Parameters			
	Descriptive stati	istics for PK parameters wil the total of TAK-906 and M	l be provided. Here, only fe will be 123.	

7.9.2 Pharmacodynamic Analysis

7.9.2.1 Serum Concentrations of prolactin level

Analysis Set:	PD Analysis Set
Analysis Variables :	Serum concentration of prolactin
Visit:	Day 1: Predose, 1, 2, 4, 6, and 24 hours post single dose.
	Days 3-6: Just before morning dose.
	Day 7: Predose, 1, 2, 4, 6, and 24 hours post morning dose.
	Day 14
Analytical Methods:	The following summaries will be provided by dose.
	(1) Summary of Serum Concentrations by Time Point

Descriptive statistics for observed values and change from Day 1predose will be provided for each time point. In addition, geometric mean, geometric standard deviations, and %CV will be provided

- (2) Concentration-time Profiles for Individual Subjects Observed values will be plotted using individual case plot.
- (3) Mean Concentration-time Profiles with Standard Deviations Mean of serum concentration will be plotted by time point using linear scale for Days 1-7, Day 1 and Day 7 respectively.
- (4) Geometric Mean Concentration-time Profiles with Geometric Standard Deviations Geometric Mean of serum concentration will be plotted by time point using natural log scale for Days 1-7, Day 1 and Day 7 respectively.

7.9.2.2 PD Parameters of Serum prolactin level

Analysis Set:	PD Analysis Set				
Analysis visit and					
Variable:	Serum concentration of prolactin				
	Visit: Day 1				
	C _{max}	t _{max}	AUC_{∞}		
	AUC _{last}	AUC ₂₄	AUC_{τ}		
	$t_{1/2z}$	λ_z			
	Visit: Day 7				
	C _{max,ss}	t _{max,ss}	$\mathrm{AUC}_{\mathrm{\tau},\mathrm{ss}}$		
	$t_{1/2z}$	λ_z			
Analytical Methods:	The following summaries will be provided by dose.				
	(1) Summary of PD Parameters				
	D • • • • • •		1 1 1 T 111		

Descriptive statistics for PD Parameters will be provided. In addition, geometric mean and %CV will be computed for C_{max} and AUCs.

(2) PD Parameters versus dose plots Plots of Cmax and AUCs versus dose levels will be prepared with individual subjects data.

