# 5.0 TRIAL OBJECTIVES AND ENDPOINTS

# 5.1 Hypothesis

This study was designated based on the following hypotheses:

- TAK-906 will be safe and well tolerated in Japanese healthy male subjects in the doses to be tested.
- Following the first dose, one or more well-tolerated doses of TAK-906 will result in a 3-fold increase in serum prolactin at the maximum level of serum prolactin (Cmax) as compared to baseline for each treatment period (single dose period, multiple dose period).

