# 6.3.3.3 PD Endpoints

The following PD parameters for serum prolactin will be derived:

- Single dose period (Day 1): AUCt, Cmax
- Multiple dose period (Day 7): AUCτ,ss, Cmax,ss

Other PD parameters maybe calculated if deemed necessary for the interpretation of data.

Serum prolactin levels will be measured as a target engagement marker. Dopamine inhibits prolactin production by pituitary lactotroph cells. When the  $D_2$  receptor is inhibited, serum prolactin levels rise and can serve as a marker for dopamine  $D_2$  receptor engagement.

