## Table 9.e Collection of Blood Samples for PD Analysis

Analyte	Matrix	Study Day	Scheduled Time	
Prolactin	Serum	1-2	Predose, 1, 2, 4, 6, and 24 hours post single dose	
Prolactin	Serum	3-6	Just before morning dose	
Prolactin	Serum	7-8	Predose, 1, 2, 4, 6, and 24 hours post morning dose	
Prolactin	Serum	14	-	

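### The SAP derives AUC-infinity, lambda-z and t1/2z from uncorrected prolactin, where they do not measure drug effect, and lists no baseline-corrected PD parameter

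*SAP*

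**What the plan says.** SAP 7.9.2.2 derives the PD parameters from serum prolactin as observed, in the PD Analysis Set. Day 1 has Cmax, tmax, AUC-infinity, AUClast, AUC24, AUC-tau, t1/2z and lambda-z. Day 7 has Cmax,ss, tmax,ss, AUC-tau,ss, t1/2z and lambda-z. No baseline subtraction or ratio is mentioned. For output: "Descriptive statistics for PD Parameters will be provided. In addition, geometric mean and %CV will be computed for" Cmax and the AUCs, and "Plots of Cmax and AUCs versus dose levels will be prepared with individual subjects data". Nothing exempts AUC-infinity from either.

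Placebo subjects stay in these tables. The corresponding PK section uses the "PK Analysis Set except subject with placebo".

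Protocol 6.3.3.3 names only AUCt and Cmax (Day 1) and AUC-tau,ss and Cmax,ss (Day 7), and permits others where interpretation requires them. It gives the purpose as "Serum prolactin levels will be measured as a target engagement marker". Protocol 5.1 states the PD hypothesis as a "3-fold increase in serum prolactin at the maximum level of serum prolactin" relative to baseline, for each treatment period.

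Baseline does enter SAP 7.9.2.1, but only for concentrations: "Descriptive statistics for observed values and change from Day 1predose will be provided for each time point". SAP 7.1.1 defines baseline as "The last evaluable observation (ie, non-missing) before the first dose of study drug". Sampling on Day 7 (Protocol Table 9.e) is "Predose, 1, 2, 4, 6, and 24 hours post morning dose", and Day 1 has the same times, so nothing is drawn between 6 and 24 h.

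**The concern.** AUC-infinity, lambda-z and t1/2z assume a concentration that decays to zero. Prolactin is made by the pituitary (Protocol 6.3.3.3) and the hypothesis is a multiple of baseline, so baseline is above zero. That the level returns to baseline once the drug effect fades is an inference, but a direct one. On that footing the terminal log-slope tends to zero and the extrapolated area has no finite limit. What the software returns depends on the subject's baseline and on a line fitted across an 18-hour gap.

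The practical risk is a PD table in which half-life seems to shorten as response grows, and an AUC-infinity plot that can put doses in the wrong order for the target-engagement marker. Meanwhile no tabulated parameter answers the only PD hypothesis in the protocol, which is each subject's peak relative to baseline.

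**Working it through.** The documents give no figure to reproduce here: no baseline prolactin, no half-life of the prolactin response, and a sample size not based on power. The check is therefore an illustration on the planned sampling times.

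**Inputs**
- Times 0, 1, 2, 4, 6 and 24 h (SAP 7.9.2.1, Protocol Table 9.e).
- Assumed baseline B = 8 ng/mL. The model scales with B, so the ordering and t1/2z do not depend on it.
- Assumed true peaks of 2, 3 and 5 times B; 3 is the protocol's hypothesised value.
- Assumed half-life of the excess over baseline, 1.5 to 11 h. The upper end equals the TAK-906 half-life in Protocol 6.3.1.

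**Formulas**
- C(t) = B + A(exp(−kt) − exp(−2t)), with k = ln 2 / half-life and A set to give the stated peak.
- AUC24 by linear trapezoid.
- lambda-z = minus the slope of ln C on time over the last three points. Choosing points by best adjusted R² gave the same results over 1.5 to 8 h.
- t1/2z = ln 2 / lambda-z.
- AUC-infinity = AUC24 + C(24)/lambda-z.

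**One case in full (3-fold peak, true half-life 1.5 h)**
- Concentrations: 8, 23.98, 20.23, 13.08, 10.02, 8.00.
- AUC24 = 15.99 + 22.11 + 33.31 + 23.10 + 162.18 = 257. The last term is the 6 to 24 h trapezoid.
- lambda-z = 0.0198, so t1/2z = 0.693/0.0198 = 35 h against a true 1.5 h.
- AUC-infinity = 257 + 8.00/0.0198 = 257 + 404 = 661. More than half is extrapolation.

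**Across cases**

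| True half-life | t1/2z (h): 2-, 3-, 5-fold | AUC-infinity: 2-, 3-, 5-fold |
|---|---|---|
| 1.5 h | 63, 35, 20.5 | 956, 661, 558 |
| 3 h | 33, 20, 12 | 638, 539, 574 |
| 8 h | 30, 19, 14 | 691, 685, 854 |

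- t1/2z falls as response rises in every case, although the true half-life is constant within each row.
- AUC-infinity for 2- versus 3-fold is reversed at 1.5 to 8.5 h but not at 9 to 11 h (801 versus 820 at 11 h).
- AUC-infinity for 3- versus 5-fold is reversed at 1.5 to 2.3 h (575 versus 543 at 2 h) but not at 2.4 to 11 h.

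**Dependence on baseline.** Hold the drug effect fixed at a 20 ng/mL excess with a 4 h half-life, and raise B from 3 to 15. t1/2z moves from 9.0 to 23.7 h, and AUC-infinity from 294 to about 1060.

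**Placebo.** For a flat profile with an assumed 15% noise, lambda-z is zero or negative in about 50% of simulated profiles. In the rest, median t1/2z is about 104 h and median AUC-infinity about 6.8 times AUC24.

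**AUC24.** Order is kept but the ratio is compressed. The 5- to 3-fold ratio is 321/257 = 1.25 at 1.5 h and reaches 1.55 at 11 h. After subtracting 8 × 24 = 192 it is 129/65 = 2.0. The straight line from 6 to 24 h overstates the excess area by 5 to 30% over 1.5 to 11 h.

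**The case against.** Several counter-arguments carry weight.

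- **The protocol allows extra PD parameters.** This is true, so there is no protocol–SAP conflict. The allowance is for parameters needed for interpretation, though, and these three do not help it.
- **Baseline is already handled.** SAP 7.9.2.1 gives change from Day 1 predose and geometric means at each time point, plus individual plots. That covers part of the need. What is missing is a subject-level ratio of Cmax to baseline, which summaries at fixed times do not supply.
- **AUC24 compression is a matter of scale.** This stands. On the difference scale nothing changes: 321 − 257 = 64 and 129 − 65 = 64. The corrected ratio of 2.0 is built in, as (5−1)/(3−1). Placebo subjects are also the right comparator for Cmax and AUC24; they are a problem only for the terminal-slope parameters.
- **Corrected AUC24 has a cost.** One predose value enters with weight 24 − 0.5 = 23.5. At 15% noise on 8 ng/mL, that is an SD of 23.5 × 1.2 = 28, against a corrected value of 65 in the 3-fold, 1.5 h case. It is a reasonable addition rather than a clear improvement.
- **The Day 7 reference is open to reading.** Protocol 5.1 could mean a baseline specific to each period. The SAP's own definitions point to Day 1 predose, but the sponsor should confirm this.

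**Conclusion.** The concern holds, as a minor point. AUC-infinity, lambda-z and t1/2z of uncorrected prolactin do not measure drug effect, and SAP 7.9.2.2 has no parameter expressed relative to baseline. The structural argument needs only that prolactin returns to a non-zero level. The sizes shown rest on assumed baseline, fold, half-life and noise values. The t1/2z distortion appeared in every case tried, while the AUC-infinity reversal occurs only over the half-lives stated.

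The consequences are limited. The PD analysis is secondary and descriptive, with no test or decision rule. Entry to Cohort 2 and its dose level rest on safety and PK data. Cmax, AUClast, AUC24 and change from Day 1 predose keep the dose order in expectation. What suffers is the reading of the PD table and of the AUC-infinity plot.

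**What to change.** In SAP 7.9.2.2:

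1. Delete AUC-infinity (Day 1) and lambda-z and t1/2z (Days 1 and 7) for prolactin.
2. Add the ratio of Cmax (Day 7: Cmax,ss) to Day 1 predose, summarised by dose with placebo shown. This is the change that matters most.
3. Add baseline-corrected AUC24 = AUC24 − 24 × Day 1 predose, noting its reliance on a single predose sample. On Day 7 AUC24 is not currently listed, but the 24 h sample is drawn and there is no evening dose, so it can be derived.
4. State that Day 1 predose is the reference on both days, in line with SAP 7.1.1 and 7.9.2.1, and have the sponsor confirm that this is the baseline meant in Protocol 5.1.
5. Keep Cmax, tmax, AUClast, AUC24, AUC-tau and the Day 7 counterparts, with a footnote that AUC24, AUC-tau and AUC-tau,ss are interpolated after 6 h.

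The cost is SAP wording and a few derived values. No samples are added, and every PD parameter named in the protocol stays.
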